7.3 Analysis Visit Windows

Refer to C4951010 Protocol Section 4.3 (Table 1) for the schedule of assessments.

Refer to the Core SAP for defining randomization days, study days, rimegepant study days, and follow-up days in Phase 2/3/4 multiple-dose studies with both DBT and OLE Phases.

Analysis visit windows are shown in Table 5.

Table 5 Analysis Visit Windows

| Analysis Period | | Analysis Day | |
|--|--|-----------------------|------------|
| Analysis Visit | Abbreviation in Listings | Analysis Visit Window | Target Day |
| Pretreatment | PRETRT | Randomization Day | |
| Screening * | | ≤ -7 | |
| Pre-Randomization * | Prerand | -6 to -1 | |
| Baseline * | | 1 | |
| Post-Randomization @ | Postrand | ≥ 2 | |
| Outcomes Research /On- Treatment Safety | Outcomes Research: DBT or OLRMG/Safety: DBT, INT, OLRMG, or ONTRT | Study Day | |
| Week 2 | | 2 to 21 | 14 |
| Week 4 | | 22 to 42 | 28 |
| Week 8 | | 43 to 70 | 56 |
| Week 12 | | 71 to 91 | 84 |
| Week 14 | | 92 to 105 | 98 |
| Week 16 | | 106 to 126 | 112 |
| Week 20 | | 127 to 154 | 140 |
| Week 24 | | 155 to 182 | 168 |
| Extension @ | | ≥ 169 | |
| Follow-Up Safety | FU | Follow-Up Day | |
| Follow-Up Week 2 | FU Week 2 | 8 to 35 | 14 |
| Follow-Up Week 8 | FU Week 8 | 36 to 77 | 56 |
| Follow-Up Extension @ | FU Ext | ≥ 78 | |

^{*} For subjects in the enrolled analysis set excluded from the full analysis set, the visit label is used for slotting. @ Denotes an extended visit in the analysis period and is displayed only in listings

Study days are used to define analysis visit windows in all analysis periods except follow-up safety. Follow-up days are used to define analysis visit windows in the follow-up safety analysis period.

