Procedure		Week 14 Visit (Day 98 +/- 3 days)	Week 16 (Day 112) and Week 20 (Day 140) Visits (both visits +/- 2 days)	Week 24 (Day 168 +/- 2 days) or EOT Visit for early discontinuation	FU Week 2 and FU Week 8 Visits (both visits +/-2 days) for all subjects4
Confirm Week 12 Laboratory Results	Х				
Concomitant Medication paper diary ⁵		х	X	Х	х
Safety Assessments					
Physical Examination ⁶			X (Week 16 only)	X	
Vital Signs / Physical Measurements ⁷		Х	X	х	х
Clinical Safety Laboratory Testing ⁸		Х		х	
Liver Function Test (LFTs)8		X	X	X	X
Lipid Panel ⁸				X	
ECG		X		X	
Urinalysis				X	
Pregnancy Test		X (urine)	X (urine)	X (urine)	X: FU W2 (urine) & FU W8 (serum)
AE, SAE, and Concomitant Procedure assessment ⁹		х	Х	Х	х
Columbia-Suicide Severity Rating Scale (C-SSRS)		Х	X	х	X (FU W2 only)

Migraine Prevention with Multiple Dosing Regimens

	Phone visit to confirm eligibility based on laboratory criterial	Open-label Extension Phase2:3			Follow-up Phase3-4
Procedure		Week 14 Visit (Day 98 +/- 3 days)	Week 16 (Day 112) and Week 20 (Day 140) Visits (both visits +/- 2 days)	Week 24 (Day 168 +/- 2 days) or EOT Visit for early discontinuation	FU Week 2 and FU Week 8 Visits (both visits +/-2 days) for all subjects4
Clinical Drug Supplies / Study Supplies					
Dispense study drug ¹⁰			х		
Administer study drug ^{10, 11}		X	х	Х	
Return used and unused study drug to site for compliance check		Х	Х	X	
Other Assessments					
Migraine-Specific Quality-of- Life Questionnaire (MSQ) v 2.1				X	
Satisfaction with Medication (SM)				X	
Clinical Global Impression- Change (CGI-c)				X	

^{1.} Study eligibility must be confirmed by Week 12 laboratory results prior to first dose of open-label study drug, which is dispensed at the Week 12 visit. Sites must contact subject by phone to confirm study eligibility prior to subject taking first dose.

² While on-study, all visit windows are used for scheduling purposes and all efforts should be made to return subjects to their original visit schedule by calculating the visit window interval from the Baseline/Randomization Visit.

^{3.} All randomized subjects who discontinue early from the Open-label Extension Phase should complete the EOT Visit. All randomized subjects should complete the Follow-up Week 2 and Follow-up Week 8 Visits.

- A Phase 4 Randomized, Double-blind, Placebo-controlled Study to Evaluate the Efficacy and Safety of Rimegepant in Episodic Migraine Prevention with Multiple Dosing Regimens

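### SAP Table 5 places Study Days 169 to 182 in both Week 24 and the listings-only Extension visit, and this SAP gives no rule for choosing between them

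*SAP*

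**What the plan says.** SAP Section 7.3, Table 5, has one block of windows that serves both outcomes research and on-treatment safety. All rows in it are counted in study days. The last two rows are "Week 24 | | 155 to 182 | 168" and "Extension @ | | ≥ 169". The footnote to the @ mark reads "Denotes an extended visit in the analysis period and is displayed only in listings".

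The follow-up block of the same table is built differently at its end. Its last visit is "Follow-Up Week 8 | FU Week 8 | 36 to 77 | 56" and its extension row is "Follow-Up Extension @ | FU Ext | ≥ 78", so there the extension begins the day after the last visit window closes.

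The protocol's schedule of open-label assessments (Section 4.3, Table 2) sets the visit as "Week 24 (Day 168 +/- 2 days) or EOT Visit for early discontinuation". Protocol Section 4.3.3.1 gives the same visit a window of plus or minus 3 days.

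SAP Section 6.4 sends safety measurements to Table 5 for slotting and refers to the Core SAP for more detail. SAP Section 6.5 sends MSQ, SM and CGI-c measurements to the same table, naming Weeks 12 and 24 as the visits to be used.

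**The concern.** Table 5 decides which visit row a value belongs to. A measurement on any of Days 169 to 182 satisfies two rows. One feeds the by-visit tables and the other appears only in listings. Two programmers could follow the table faithfully and produce different Week 24 results.

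The overlap begins one day after the Week 24 target, so ordinary visits inside the protocol window can reach it. Week 24 is the last scheduled on-treatment time point. At stake are the Week 24 rows of the laboratory, vital-sign and ECG change-from-baseline tables (SAP Sections 6.4.2.3, 6.4.3.1 and 6.4.4.1). The open-label MSQ, SM and CGI-c summaries (SAP Sections 6.5.1 to 6.5.3), which support exploratory objectives 10 to 12, may also be affected.

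**Working it through.** **Inputs.** Target days and windows come from SAP Table 5. The protocol visit windows come from Protocol Table 2 (Day 168 ± 2) and Protocol Section 4.3.3.1 (Day 168 ± 3).

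**Step 1: reproduce the Week 24 window.** The SAP does not state how the windows were built, but a midpoint rule fits. Each upper bound is the midpoint between a target and the next target. Each lower bound is the previous upper bound plus 1. The first lower bound, Day 2, is taken from the table. The last window is closed by adding half the gap to the previous target.

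- Week 2: 2 to (14 + 28)/2 = 21
- Week 4: 22 to (28 + 56)/2 = 42
- Week 8: 43 to (56 + 84)/2 = 70
- Week 12: 71 to (84 + 98)/2 = 91
- Week 14: 92 to (98 + 112)/2 = 105
- Week 16: 106 to (112 + 140)/2 = 126
- Week 20: 127 to (140 + 168)/2 = 154, matching "Week 20 | | 127 to 154 | 140"
- Week 24: 155 to 168 + (168 − 140)/2 = 182

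All eight agree with Table 5. The same rule gives the follow-up bounds: (14 + 56)/2 = 35 and 56 + (56 − 14)/2 = 77. The Week 24 window is thus consistent with the rest of the table, and the Extension start is the cell that does not fit. Its value equals the Week 24 target plus 1 (168 + 1 = 169), whereas the follow-up block uses the window end plus 1 (77 + 1 = 78).

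**Step 2: measure the overlap.**

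- Overlap: Days 169 to 182, which is 182 − 169 + 1 = 14 days.
- Week 24 window: 182 − 155 + 1 = 28 days.
- Share of the window: 14/28 = 50%.
- Between each of the other consecutive on-treatment windows, the next lower bound is exactly one day after the previous upper bound, so none of them overlap.

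**Step 3: check whether compliant visits reach it.** This takes the protocol day and the SAP study day as the same count; both place Week 24 at Day 168.

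- Under ± 2 days, the permitted days are 166 to 170. Days 169 and 170 are in the overlap: 2 of 5 (40%).
- Under ± 3 days, the permitted days are 165 to 171. Days 169 to 171 are in the overlap: 3 of 7 (43%).

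These are shares of permitted calendar days. The documents contain no visit-timing data that would turn them into a share of records.

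**Step 4: trace the outputs if Extension were applied.**

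- Laboratory, vital-sign and ECG by-visit tables show scheduled visits through Week 24 and also an end-of-treatment (EOT) value. The Week 24 row would lose the measurement; the EOT row may retain it, by a rule held in the Core SAP.
- Open-label MSQ, SM and CGI-c tables show Week 24 only, so they have no second row to hold the value.
- Adverse events, worst laboratory abnormality, LFT elevations, vital-sign and ECG abnormalities and C-SSRS are tabulated by analysis period, so visit windows do not enter.
- The primary and key secondary efficacy endpoints use eDiary data through Day 84, and the MSQ secondary endpoint uses the Week 12 window (Days 71 to 91). None reaches Day 169.

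**Step 5: test the correction.** With Extension at Day 183 or later, no day from 155 to 182 qualifies for both rows, and the overlap is 0 days.

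**The case against.** The overlap itself is plain on the face of the table. The case on the other side concerns its consequences, and most of it stands.

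First, SAP Section 6.4 refers to the Core SAP for measurement slotting in general. A tie-break could exist there, so the safety tables may not be ambiguous in practice. The rules that this SAP names elsewhere concern several values in one window or on one date, which is a different problem from one value in two windows. The possibility still cannot be excluded.

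Second, Section 6.5 names only Weeks 12 and 24 for the outcomes measures. That is more specific than a shared block of Table 5 and can fairly be read as putting Days 169 to 182 in Week 24. Section 6.5 also provides a by-subject listing only for MSQ, so a listings-only label would have nowhere to appear for SM and CGI-c. The text leans towards Week 24 here without expressly setting the Extension row aside.

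Third, intent is easy to infer from the follow-up rows, and a careful programmer would probably assign these days to Week 24.

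A reader might go further and infer that about 40% of Week 24 data would be lost, that the loss would be non-random because it falls on later attenders, or that these values would vanish from the tables altogether. The documents support none of these. The 40% and 43% count calendar days and would equal a share of visits only if attendance were even. Nothing links attendance on Day 169 rather than Day 168 to outcome. The EOT row may also preserve the laboratory, vital-sign and ECG values. Nor is every late measurement ambiguous: from Day 183 only Extension applies.

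**Conclusion.** The contradiction is certain. Study Days 169 to 182, half of the Week 24 window, belong to two visits with different reporting, and this SAP contains no precedence rule. Visits that comply with the protocol can fall there.

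The effect is conditional and limited. If those days are programmed as Extension, the Week 24 rows of descriptive laboratory, vital-sign and ECG tables lose values that the EOT row may still show. The Week 24 MSQ, SM and CGI-c summaries could lose values outright, though Section 6.5 points the other way. No confirmatory result and no period-based safety result changes. The number of affected records cannot be estimated from the documents.

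This rests on two assumptions: that the unseen Core SAP holds no overriding tie-break, and that protocol days and SAP study days coincide. The point is minor, but worth correcting because it is an operative rule and the correction is clear.

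**What to change.** In SAP Table 5, change the Extension window to Study Day 183 or later, so that it starts the day after Week 24 ends, as the follow-up block already does. Ending Week 24 at Day 168 would also remove the overlap, but it would break the pattern of the other windows and push compliant visits on Days 169 and 170 (or 169 to 171) out of Week 24.

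If the Core SAP already has a rule for a value that falls in two windows, cite it in Section 7.3. One sentence in Section 6.5 could confirm that Extension is not used for MSQ, SM or CGI-c summaries. The two protocol windows for the Week 24 visit (± 2 days in Table 2, ± 3 days in Section 4.3.3.1) contradict each other and should be reconciled.

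The Table 5 correction costs one cell, with no new data and no change to any hypothesis test. It should be made before the by-visit tables are finalised.

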8 CONTENTS OF REPORTS

All TLFs described in this SAP are produced for the LSLV final CSR (see Section 1.2).

9 APPENDICES

9.1 Relevant Protocol Deviations

Relevant eligibility protocol deviations include the following categories:

- Previously treated with study drug in another multiple-dose BHV3000 study. Defined as subjects with (1) previous BHV3000 study subject identifiers from studies BHV3000-201/305/405/406/407 from the Demographics/Informed Consent CRF, and (2) who took ≥ 1 dose of study drug (e.g., rimegepant or placebo) in a multiple-dose study.
- Randomized or treated with study drug under > 1 subject identifier. These are identified from the Protocol Deviations CRF.
- Migraine history issue, defined as any of the following subcategories:
 - $0 \le 3$ or ≥ 15 migraine days per month of any pain intensity in the 3 months prior to screening
 - \circ \geq 15 headache days per month in the 3 months prior to screening.

These are based on the Migraine History CRF.

- Finding out of range during pretreatment, defined any as any of the following subcategories:
 - o Females with a positive pregnancy test (see Section 6.4.2)
 - Estimated glomerular filtration rate (eGFR) according to the re-expressed abbreviated (4-variable) Modification of Diet in Renal Disease (MDRD) Study equation ≤ 40 mL/min/1.73m², if originally consented to Protocol Version 4 or lower *
 - eGFR according to the re-expressed abbreviated (4-variable) MDRD Study equation < 30 mL/min/1.73m², if originally consented to Protocol Version 5 or higher *
 - o BMI \geq 33 kg/m², if originally consented to Protocol Version 4 or lower *
 - o BMI > 35 kg/m², if originally consented to Protocol Version 5 or higher *
 - C-SSRS suicidal ideation with active intent or plan to act, or suicidal behavior present during pretreatment. Defined as having a "yes" response to any of the following C-SSRS questions:
 - Suicidal ideation question 4 (active suicidal ideation with some intent to act, without specific) or 5 (active suicidal ideation with specific plan and intent)
 - Suicidal behavior question 1 (actual attempt), 3 (interrupted attempt), 4 (aborted attempt), 5 (preparatory acts or behavior), or 6 (suicidal behavior).

For the subcategories marked with "*", all nonmissing values during the pretreatment analysis period must meet the deviation criteria in order to be considered a deviation.

- Efficacy data issue during the first 28 days of the OP, defined as any of the following subcategories:
 - \circ \leq 3 migraine days
 - ≥ 15 headache days
 - \circ \leq 23 days of eDiary efficacy data (see Sections 6.2.6.2 and 9.2.2).

These are assessed during the 28-day OP analysis period (see Section 7.2). Migraine days and headache days are absolute, not prorated to 28 days per month (see Sections 9.2.5 and 9.2.6), and of total pain intensity.

Relevant subject management protocol deviations include the following categories:

- Randomization stratum discrepancies between IWRS and actual data, defined as any of the following subcategories:
 - IWRS randomization stratum of yes, but no use of nonstudy previous medication for migraine prevention generally considered to have efficacy
 - IWRS randomization stratum of no, but use of nonstudy previous medication for migraine prevention generally considered to have efficacy.

See Section 6.2.5.4 for the definition of nonstudy medication for migraine prevention generally considered to have efficacy.

- DB study drug dosing noncompliance, defined as any of the following subcategories (see Section 6.2.6.2):
 - DB study drug taken but not randomized
 - DB tablet count compliance < 80% from DB study drug start to later of last scheduled DBT Phase visit or DB study drug end/OL rimegepant start
 - > 1 DB tablet taken on any 1 day
 - Incorrect DB study drug taken
- OL rimegepant dosing noncompliance, defined as any of the following subcategories (see Section 6.2.6.2):
 - o OL rimegepant tablet count compliance < 80% from OL rimegepant start to later of last scheduled OLE Phase visit or OL rimegepant end
 - > 1 OL rimegepant tablet taken on any 1 day
 - OL rimegepant start on or before DB study drug end
 - o OL rimegepant taken but DB study drug never taken
- eDiary usage compliance < 80% from DB study drug start to later of last scheduled DBT Phase visit or DB study drug end (see Section 6.2.6.2)
- Prohibited nonstudy medications taken on or after informed consent (or otherwise specified), defined as any of the following subcategories:

- Atypical antipsychotic, divalproex, valproic acid, or valproate #
- Ergotamine
- Lamotrigine
- Medication for migraine prevention generally considered to have efficacy or prophylactic migraine medication taken up to 30 days before informed consent or afterward (see Sections 6.2.5.4 and 6.2.6.3) #
- Narcotic (barbiturate or opioid) #
- Select moderate or strong cytochrome P450 3A4 (CYP3A4) inducer #
- Select strong CYP3A4 inhibitor #.

For the subcategories marked with "#", preferred names are displayed alphabetically as additional subcategories. Medications taken up to X days before a reference date or afterward are defined as those with imputed medication start date or imputed end date \geq reference date -X. Refer to the Core SAP for additional details about prohibited nonstudy medications.

The IWRS randomization date is the reference date for "randomization". If the IWRS randomization date is missing, then the study drug start date is used.

The protocol version to which subjects originally consented is determined from the Demographics/Informed Consent CRF.

9.2 eDiary Efficacy

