4.3.1.2 Pre-randomization Evaluation Visit

Subjects must return to the study site for the Pre-randomization Evaluation Visit within 4 days + 2 days of the Baseline Visit. Note that the "+ 2 days" window is included *for scheduling purposes only*. Every effort should be made to complete the Pre-randomization Evaluation Visit as close to, and within, the 4 days prior to the Baseline Visit as possible. However, for scheduling convenience, this window may be up to 6 days between the Pre-randomization Evaluation Visit and the Baseline Visit.

Safety labs, and an assessment of how the subject is feeling will be performed, a urinalysis will be completed, a serum pregnancy test, where applicable, will be obtained, an ECG will be performed, a brief physical exam (PE) will be performed unless a full PE is clinically warranted, vital signs and physical measurements will be performed according to Table 1, and compliance with the concomitant mediation paper diary and eDiary will be assessed.

If the subject continues to meet study entry criteria and laboratory test results are acceptable per protocol, then the subject will be randomized at the Baseline Visit into the Double-blind Treatment Phase.

If the laboratory results are not acceptable per protocol, then the subject is determined to be a screen failure and should be recorded as such in IWRS. The subject must return to the study site to return the eDiary.

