- Subject has current diagnosis of major depressive disorder requiring treatment with atypical antipsychotics, schizophrenia, bipolar disorder, or borderline personality disorder.
- o) Body mass index > 35.0 kg/m².

- History of anaphylaxis to any substance or a clinically important reaction to any drug.
- Sex and Reproductive Status
 - a) WOCBP who are unwilling or unable to use an acceptable contraceptive method or abstinence to avoid pregnancy for the entire study and for 60 days after the last dose of study drug.
 - b) Women who are pregnant or breastfeeding.
 - Women with a positive pregnancy test at screening or prior to study drug administration.
- ECG and Laboratory Test Findings
 - a) Estimated glomerular filtration rate (eGFR) according to the re-expressed abbreviated (four-variable) Modification of Diet in Renal Disease (MDRD) Study equation ≤ 30 ml/min/1.73m².
 - Abnormal ECG that in the investigator's opinion makes the subject unsuitable for a clinical trial (e.g. Corrected QT interval > 470 msec, Left Bundle Branch block)
 - c) Total serum bilirubin > 1.5 x ULN.
 - d) AST or ALT > 1.5 x ULN.
 - e) Serum albumin < 2.8 g/dL.
 - f) Neutrophil count ≤ 1000/μL (or equivalent)
 - g) HbA1c > 7.5%
- 6. Prohibited Medications
 - a) Medication for migraine prophylaxis generally considered to have efficacy, regardless of indication, taken within 30 days prior the Screening Visit (see Section 16.5 Appendix 5).
 - b) Analgesics (e.g., nonsteroidal anti-inflammatory drugs [NSAIDs] or acetaminophen) taken ≥ 15 days per month during the 3 months (12 weeks) prior to the Screening Visit.
 - c) Medication accepted for treatment of acute migraine (Section 5.5.1) for a non-migraine indication taken ≥ 15 days per month during the 3 months (12 weeks) prior to the Screening Visit.
 - Low dose aspirin (up to 100mg daily) for documented cardiovascular prophylaxis is allowed.

- d) Biologic migraine medication (such as CGRP monoclonal antibodies listed in Section 16.5 Appendix 5) taken during the 6 months (24 weeks) prior to the Screening Visit.
- e) Prohibited medication or device used during the Observation Phase (see Section 5.4).

Other Exclusion Criteria

- a) Prisoners or subjects who are involuntarily incarcerated.
- Subjects who are compulsorily detained for treatment of either a psychiatric or physical (e.g., infectious disease) illness.

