- c) Non-compliance with or inability to complete eDiary during Observation Phase. Subjects with less than 24 completed eDiary reports during 28 days in the Observation Phase will not be considered for participation due to non-compliance with the eDiary.
- d) Exposure to non-biological investigational agents within the 30 days prior to the Screening Visit.
- e) Exposure to biological investigational agents such as monoclonal antibodies within the 6 months (24 weeks) prior to the Screening Visit.
- f) Subjects who meet criteria for C-SSRS Suicidal Ideation Items 4 or 5 within the last 12 months prior to the Screening Visit, OR subjects who endorse any of the 5 C-SSRS Suicidal Behavior Items (actual attempt, interrupted attempt, aborted attempt, preparatory acts, or behavior) within the last 10 years prior to the Screening Visit, OR subjects who, in the opinion of the investigator, present a serious risk of suicide (See Section 6.2.5).
- g) Previous enrollment in any multiple dose BHV3000 (rimegepant) study, such as BHV3000-201, BHV3000-305, BHV3000-405, BHV3000-406, or BHV3000-407, regardless of the number of doses taken. Subjects may be considered for BHV3000-404 if the subject participated in any of the following single dose studies: BHV3000-301, BHV3000-302, BHV3000-303, but did not participate in any multiple dose rimegepant study. Note that subjects who were considered screen failures in a past BHV3000 study may be considered after discussion with the Sponsor and written approval is received.
- h) Subjects are excluded if they have had no therapeutic response with > 2 of the 8 medication categories for prophylactic treatment of migraine listed in Appendix 4 after an adequate therapeutic trial. Additional details can be found in Section 16.4 Appendix 4.
- i) Participation in any other investigational clinical study while participating in this clinical study. Participation in a COVID-19 mRNA vaccine study (vaccine must be authorized

under FDA emergency use authorization or approval) who are at least 30 days post last dose of the vaccine are permitted to be screened for this study.

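### SAP 9.1 under-counts eGFR and BMI eligibility breaches in the programmed relevant-deviation table and listing

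*SAP*

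**What the plan says.** SAP 9.1 defines a programmed list of relevant protocol deviations. SAP 6.2.4.1 reports it as a frequency table by treatment group and overall, and as a by-subject listing, both for the full analysis set.

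Within the category for pretreatment findings out of range, the eGFR and BMI rows carry an asterisk. For those rows, "all nonmissing values during the pretreatment analysis period must meet the deviation criteria in order to be considered a deviation". The eGFR row for the current protocol reads "eGFR according to the re-expressed abbreviated (4-variable) MDRD Study equation < 30 mL/min/1.73m², if originally consented to Protocol Version 5 or higher".

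The protocol states the matching rules as follows.

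- Section 5.3, exclusion 5a, excludes a value on the "Modification of Diet in Renal Disease (MDRD) Study equation ≤ 30 ml/min/1.73m²". Exclusion 2o excludes BMI above 35.0 kg/m².
- Section 4.3.1.1 makes a subject who does not meet the entry criteria at Screening a screen failure.
- Section 4.3.1.2, on the next visit, says: "If the laboratory results are not acceptable per protocol, then the subject is determined to be a screen failure".

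A neighbouring SAP row covers earlier multiple-dose rimegepant studies. It counts only subjects "who took ≥ 1 dose of study drug (e.g., rimegepant or placebo) in a multiple-dose study". Exclusion 7g applies "regardless of the number of doses taken", but it also lets screen failures from an earlier study be considered with written sponsor approval.

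**The concern.** The protocol tests eligibility at more than one visit, and nothing in it lets an acceptable eGFR at one visit cancel an exclusionary one at another. Where the protocol addresses repeat testing it says so: blood pressure may be repeated once, and a drug screen showing cocaine, amphetamine or phencyclidine may not be retested. No repeat provision is stated for eGFR or BMI. The all-values rule works the other way, because one acceptable pretreatment value removes the deviation even if the exclusionary value is the one closest to dosing. The SAP gives no reason for it.

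The eGFR limit looks like a slip. The SAP revision history for Version 3 says the eGFR and BMI criteria were edited to agree with Protocol Version 5 Section 5.3, and the row for earlier consents uses ≤ 40.

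At stake is the accuracy of the by-group table of eligibility breaches, which includes a renal-function limit.

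**Working it through.** The plan states no figure on this point, so the check applies both rules to example values.

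**Inputs.** Serum chemistry, which includes eGFR (Protocol 6.2.4.1), has two scheduled pretreatment values, Screening and Pre-randomization (Protocol Table 1; SAP 6.4.2). Weight, and so BMI, has three: Screening, Pre-randomization and Baseline (Protocol Table 1; SAP 6.4.3).

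**Rules for eGFR, Version 5 consent.**
- Protocol: ineligible if any value ≤ 30.
- SAP 9.1: deviation if all values < 30.

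| eGFR (Screening, Pre-randomization) | Protocol: any ≤ 30 | SAP: all < 30 | Limit corrected only: all ≤ 30 | Rule corrected only: any < 30 | Last value ≤ 30 |
|---|---|---|---|---|---|
| 28, 28 | ineligible | flagged | flagged | flagged | flagged |
| 45, 25 | ineligible | missed | missed | flagged | flagged |
| 28, 45 | ineligible | missed | missed | flagged | missed |
| 30, 30 | ineligible | missed | flagged | missed | flagged |
| 30, 28 | ineligible | missed | flagged | flagged | flagged |
| 31, 31 | eligible | no flag | no flag | no flag | no flag |

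Neither correction alone closes the gap. Any value ≤ 30 flags all five ineligible pairs. A last-value rule still misses 28 followed by 45.

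**Rules for BMI, Version 5 consent.** The limit is > 35 in both documents, so only the all-values condition matters.

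| BMI (Screening, Pre-randomization, Baseline) | Any > 35 | SAP: all > 35 |
|---|---|---|
| 35.4, 35.4, 35.4 | yes | flagged |
| 35.4, 34.9, 35.2 | yes | missed |
| 34.9, 35.2, 35.3 | yes | missed |
| 35.0, 35.0, 35.0 | no | no flag |

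**Size, on assumptions only.** Let p be the chance that a single value breaches, and k the number of values. Among subjects with at least one breach, the share flagged by an all-values rule is the mean of p^k divided by the mean of 1 − (1 − p)^k. I assume independent normal error and true values spread evenly around the limit. Neither the within-subject CV nor the spread is in the documents. The eGFR rows use ≤ 30 throughout, which isolates the all-values rule.

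| Parameter | Assumed CV | Spread of true values | Share flagged |
|---|---|---|---|
| eGFR, k = 2 | 6% | ±3 / ±5 / ±10 | 0.53 / 0.67 / 0.82 |
| eGFR, k = 2 | 10% | ±3 / ±5 / ±10 | 0.425 / 0.53 / 0.71 |
| BMI, k = 3 | 0.5% | ±0.5 / ±2 | 0.54 / 0.86 |
| BMI, k = 3 | 1% | ±0.5 / ±2 | 0.31 / 0.74 |

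The share depends heavily on how closely subjects are assumed to sit to the limit. It also ignores that most breaching subjects should be stopped before randomisation. It shows the direction of the error and is not an estimate for this trial.

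**The case against.** The strongest reply is that SAP 9.1 is a chosen list and not an audit of every criterion. It has no row for exclusionary bilirubin, transaminases, albumin, neutrophils, HbA1c, ECG or blood pressure. An openly stated rule within such a list is partly a design choice, perhaps meant to tolerate a re-test. That explains why a rule might exist. It does not explain a limit that differs from the one the SAP says it follows, or why an acceptable earlier value should cancel the later one.

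A reader might infer that the affected subjects are reported as having no deviation at all, so that eligibility appears to have been kept. The documents do not support that. SAP 6.2.4.2 separately lists deviations that sites mark as significant, with the inclusion/exclusion number, and Protocol 5.8 requires significant departures from the entry criteria to be documented. That safeguard is partial: it depends on the site's own marking, and it is a listing, not a table by group.

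Three further limits stand.

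- The BMI argument is weaker. The screen-failure sentence in Protocol 4.3.1.2 concerns laboratory results, exclusion 2o names no visit, and Table 1 marks the entry-criteria review at Screening and Baseline only. A breach at the Pre-randomization weight alone is not clearly a screen failure.
- The eGFR limit mismatch concerns only subjects consented to Version 5 or higher.
- It is tempting to say the prior-study row should simply lose its dosing condition. Exclusion 7g permits approved earlier screen failures, and those subjects could then be flagged wrongly. The true gap is subjects enrolled in an earlier multiple-dose study, not screen-failed there, and never dosed.

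**Conclusion.** The point holds as a reporting defect of minor severity. The programmed table and listing under SAP 6.2.4.1 will miss a randomised subject whose eGFR was exclusionary at one pretreatment visit but not the other. For Version 5 consents they will also miss a subject whose eGFR was exactly 30, even if every value was 30. BMI is affected by the all-values rule only.

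No analysis set in SAP 4.1 is defined by relevant deviations, so a reader should not infer any effect on the efficacy or safety results. The number of subjects cannot be derived from the documents. It is probably small, because only subjects randomised despite an exclusionary value are concerned. The eGFR conclusion rests on reading Protocol 4.3.1.1 and 4.3.1.2 as making any one exclusionary result sufficient, which is how both sections are worded.

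**What to change.** In SAP 9.1, before the database lock:

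1. Change the eGFR criterion for Version 5 consents from < 30 to ≤ 30, so that it matches Protocol 5.3 exclusion 5a.
2. Replace the all-values rule for eGFR and BMI with one that flags any exclusionary value at a scheduled pretreatment eligibility visit, and name the visits for each parameter. At minimum, use the last value on or before randomisation, accepting that an exclusionary Screening value followed by an acceptable one is then not counted. Reconcile the wording with Protocol 4.3.1.1, 4.3.1.2 and 5.3, and say how unscheduled repeats are treated. If the sponsor prefers to keep the all-values rule, the SAP should give the reason and footnote the table.
3. Keep the dosing condition in the prior-study row. If fuller coverage of exclusion 7g is wanted, add a separate row for subjects enrolled in an earlier multiple-dose study but not dosed, leaving out earlier screen failures admitted with written sponsor approval.

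The first two changes need SAP wording and a few lines of programming, with no new data. The third needs a way to identify earlier screen failures, which the SAP does not describe. The drawback is that the reported deviation count may be slightly less favourable.
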